they complied with their assigned treatments (Gupta, 2011). Most likely, not all participants will comply with their assigned treatments and missing data will be an issue. To ensure a conservative estimate of treatment effects (and to avoid confounds of patient characteristics with treatment allocation) ITT analyses were used. We planned to report information on participants who deviated from their random allocation treatment, but no participants deviated into another group. We also reported information on missing data. Specifically, according to CONSORT guidelines we reported “numbers analysed” (number of participants included in each analysis and whether the analysis was by original assigned groups; Schulz, Altman, & Moher, 2010, p. 727).

Missing data. We used full information maximum likelihood (FIML) to handle missing data. FIML is superior to other traditional approaches, such as listwise deletion, as it uses all available information in all observations instead of deleting observations due to missing values (Muthén & Muthén, 2007). Furthermore, as described above, we conducted analyses to investigate if participants who dropped out of the study differed systematically from those who remained in the study. Key characteristics were identified and were controlled for in all analyses.

Randomization. Following baseline data collection, all participants were randomly assigned (see information on blinding below) to either the MBST intervention or the psychoeducational intervention. Randomization represents best practices in research and aims to ensure that each participant is no more likely than the next to be assigned to a particular group. Specifically, we used restricted random allocation to ensure equally-sized groups. To do this the lab coordinator gave the co-PI fake participant IDs for the semester in an excel spreadsheet (e.g., a list of 50 participants with IDs such as 134, 258, 250, 350). The co-PI randomly selected half of the fake participant IDs to be assigned to one group and another half to be assigned to the

other group. The co-PI then gave the list back to the lab coordinator who paired the fake participant IDs with the real participant IDs. The lab coordinator then randomly assigned each group to a condition. This procedure was repeated for each semester. The co-PI did not see any real participant IDs until all data collection was completed and the co-PI did not know which participant IDs or numbers corresponded to which treatment group until all analyses were finished.

Blinding. While randomization is one important step in minimizing bias, randomization alone does not solve all issues of bias. Another important factor to consider is blinding, which refers to “the concealment of group allocation from one or more individuals involved in a...randomized controlled trial.” (Karanikolas, Farrokhyar, & Bhandari, 2010, p. 345) If a member of the research team (who is also aware of the hypotheses) knows which participants are assigned to which groups, it can lead to bias throughout the process. For example, a researcher may treat an individual in one treatment group (in this case, the MBST intervention) differently as compared to a participant in another group (the psychoeducational intervention) and this might influence the participants to behave in a way that is in line with the researcher’s hypotheses during assessments. Bias can also be introduced later on in the research process during data analysis. If a researcher knows which group is hypothesized to perform better, the researcher may selectively report results of statistical tests. Therefore, it is critical to blind the researchers throughout as much of the process as possible.

To reduce bias, a few steps were taken (some of which were already mentioned above). First, the co-principal investigator did not see any participant names/emails throughout the data collection process. All participants completed assessments online using their email addresses. A separate researcher (lab coordinator) downloaded the data and assigned participant IDs to the

participants based on their email addresses. The lab coordinator then deleted the email addresses from the data files before the co-principal investigator ever had a chance to look at them. The co-principal investigator then randomized participants' fake IDs using excel (see process described above). Following that, the co-principal investigator gave the lab coordinator the list of fake participant IDs who have been assigned to equal groups. The lab coordinator then paired the fake IDs with the real IDs and randomly assign groups to treatment conditions. The values of corresponding conditions were not be shown to the co-principal investigator until all data has been collected and all analyses have been conducted. Additionally, the lab coordinator sent and responded to all participant emails as to keep the co-principal investigator blind during this process as well (since IDs were matched to email addresses). The same process for deleting email addresses and assigning participant IDs was conducted at follow-up.

During the actual intervention, the co-principal investigator was not allowed to handle any intervention materials, as to keep her blinded from IDs. However, as the co-principal investigator was part of the actual intervention it must be acknowledged that she was not fully blinded throughout this process.

During data analysis, precautions were made to keep the co-principal investigator blind as well. As stated above, all analyses were determined a-priori. Therefore, the co-principal investigator could not selectively test and/or report analyses but reported as stated in the document. As previously mentioned, when running analyses with the dummy coded variables the co-principal investigator did not know which number corresponded to which treatment group. The value of the groups was not revealed to her until all analyses were conducted.

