Aim 2. To assess the effectiveness of the MBST intervention at increasing mindfulness skills. As a manipulation check, we investigated whether the MBST intervention improved mindfulness skills. We hypothesized that participants in the MBST intervention would increase mindfulness skills from baseline (before the intervention) to follow-up (after the intervention). Specifically, we hypothesized that participants in the MBST intervention would increase their ability to observe, describe, accept without judgment, and act with awareness.

Aim 3. To assess the effectiveness of the MBST intervention at improving emotion regulation. As a manipulation check, we investigated whether the MBST intervention improved emotion regulation. We hypothesized that participants in the MBST intervention will improve emotion regulation skills from baseline (before the intervention) to follow-up (after the intervention). Specifically, we hypothesized that participants in the MBST intervention would improve their emotional awareness, emotional clarity, acceptance of emotional responses, impulse control, access to emotion regulation strategies, and ability to engage in goal-directed behavior.

Aim 4. To evaluate the effectiveness of the MBST intervention (treatment) and psychoeducational intervention (active control) at reducing the perpetration of dating violence (physical, sexual, and psychological).

Aim 4a. To assess the effectiveness of the psychoeducational intervention at reducing the perpetration of dating violence. Before comparing the effectiveness of the interventions against one another, we first planned to assess each intervention

individually. We hypothesized that the psychoeducational intervention would reduce dating violence perpetration (physical, psychological, and sexual) from baseline (before the intervention) to follow-up (after the intervention); however, given the evidence that psychoeducational interventions are largely ineffective we did not expect the reduction to be statistically significant.

Aim 4b. To assess the effectiveness of the MBST intervention at reducing the perpetration of dating violence. We hypothesized that the MBST intervention would significantly reduce dating violence perpetration (physical, sexual, and psychological) from baseline (before the intervention) to follow-up (after the intervention).

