Aim 4c. To assess the effectiveness of the MBST intervention compared to a psychoeducational intervention (active control) at reducing the perpetration of dating violence. We hypothesized that the MBST intervention will be more effective at reducing dating violence perpetration (physical, sexual, and psychological) as compared to the psychoeducational intervention.

Methods

Participants

100 participants were recruited through Kent State University's online subject pool. Sample size was determined using G*Power3 (Faul, Erdfelder, Lang, & Buchner, 2007). Ninety-one participants completed the initial baseline assessment, and three participants were excluded from the rest of the study for not meeting inclusion criteria (see below; 2 indicated being single, 1 indicated being married). Thus, this study reports on the remaining 88 participants' data.

To be eligible, participants were required to be over the age of 18, in a current dating relationship (of 6 months or longer) and were required to confirm that they had *not* been

diagnosed with psychopathology (Major Depressive Disorder, Post-Traumatic Stress Disorder, Borderline Personality Disorder). At baseline, participants did not differ between assigned treatment groups based on age, ethnicity, gender, depression, anxiety, externalizing behavior problems, or substance use.

Furthermore, only one member of the dating couple could participate in the study. To address issues surrounding contamination, participants were reminded throughout the course of the study that they could not discuss the intervention with anyone (except their romantic partner) until the end of the study.

Data collection was conducted online (except for the first two homework assignments which were handed in using paper copies, used for compliance data; see Data and Safety Monitoring Plan for details surrounding homework collection). Participants were asked to complete online surveys in private, though they could choose where that was (e.g., dorm room or elsewhere). The actual intervention took place on Kent State University's campus, specifically classrooms in Kent Hall (rooms 60, 102, 145, and 167). This study was approved by Kent State University's Institutional Review Board.

Trial design

This study utilized a two-armed, parallel-design. The allocation ratio was 1:1. The treatment group was the MBST intervention and the active control group was the psychoeducational intervention.

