Aim 3. To assess whether participants in the MBST intervention improved their emotion regulation (a manipulation check), we examined mean differences using paired t-tests with covariates. These tests compared the means of emotion regulation subscales at baseline to the mean of emotion regulation subscales at follow-up, controlling for covariates identified in preliminary analyses. Please note this analysis only included participants who were assigned to the MBST intervention (and did not include those in the psychoeducational intervention). Tests were run individually for all six subscales (lack of emotional awareness [DER – EA], lack of emotional clarity [DER – EC], nonacceptance of emotional responses [DER – NE], impulse control difficulties [DER – IC], limited access to emotion regulation strategies [DER – ER], and difficulties engaging in goal-directed behavior [DER – DE]). Please note that a *decrease* in means indicates improvement, as higher scores on the Difficulties in Emotion Regulation Scale indicate more problems with emotion regulation.

Aim 4a. To assess whether participants in the psychoeducational intervention reduced dating violence perpetration from baseline (before the intervention) to follow-up (after the intervention) we examined paired t-tests with covariates. These tests compared the mean of dating violence perpetration at baseline to the mean of dating violence perpetration at follow-up, controlling for covariates identified in preliminary analyses. Please note this analysis only included participants who were assigned to the psychoeducational intervention (and did not include those in the MBST intervention). Please also note analyses were run separately for each type of dating violence (physical, sexual, psychological).

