Aim 4b. To assess whether participants in the MBST intervention reduced psychological dating violence perpetration from baseline (before the intervention) to follow-up (after the intervention) we examined mean differences using paired t-tests with covariates. These tests compared the mean of dating violence perpetration at baseline to the mean of dating violence perpetration at follow-up, controlling for covariates identified in preliminary analyses. Please note this analysis only included participants who were assigned to the MBST intervention (and did not include those in the psychoeducational intervention). Please also note analyses were run separately for each type of dating violence (physical, sexual, psychological).

Aim 4c. We used a regression framework to investigate the effectiveness of the MBST intervention at reducing dating violence perpetration as compared to the psychoeducational intervention. We chose to run my analyses within a regression framework in Mplus as this allowed for intercorrelations among predictors (e.g., anxiety and depression were included as covariates so we could account for their intercorrelation) and the use of FIML to handle missing data. We used dummy coding to create a variable to differentiate treatment groups. Within a regression framework, we used this dummy-coded variable to predict our outcome (dating violence). We controlled for baseline levels of dating violence perpetration and included other covariates based on preliminary analyses. This analysis, as compared to the analyses for Aims 1 – 3, included participants from both groups. Please also note analyses were run separately for each type of dating violence (physical, sexual, psychological).

Intent to treat analyses. As guided by the Consolidated Standards of Reporting Trials (CONSORT; Schulz, Altman, & Moher, 2010), the number of participants in each group were analyzed according to the intent-to-treat (ITT) principle. ITT is a collective strategy for design, conduct, and analysis in which all participants who are randomized to a group are treated as if

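### Aims 4a and 4b judge effectiveness by separate within-arm significance tests, which do not compare the arms, and the plan does not say that Aim 4c governs if it disagrees

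*Combined protocol and SAP*

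**What the plan says.** Under Aims and Hypotheses, Aim 4a expects perpetration to fall in the psychoeducational arm but adds: "given the evidence that psychoeducational interventions are largely ineffective we did not expect the reduction to be statistically significant". Aim 4b makes the opposite prediction about significance: "We hypothesized that the MBST intervention would significantly reduce dating violence perpetration (physical, sexual, and psychological) from baseline". Both are worded as assessments of an intervention's effectiveness, and both come before the comparison of arms.

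The Analysis Plan gives each aim its own within-arm test. The Aim 4a paragraph begins "To assess whether participants in the psychoeducational intervention reduced dating violence perpetration from baseline (before the intervention) to follow-up" and restricts the data: "Please note this analysis only included participants who were assigned to the psychoeducational intervention (and did not include those in the MBST intervention". The Aim 4b paragraph says "we examined mean differences using paired t-tests with covariates" and is restricted to the MBST arm. For each aim, "Please also note analyses were run separately for each type of dating violence (physical, sexual, psychological".

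Aim 4c is the comparison of arms. Its hypothesis is "We hypothesized that the MBST intervention will be more effective at reducing dating violence perpetration" than the control. Its analysis uses both arms and adjusts for baseline perpetration: "Within a regression framework, we used this dummy-coded variable to predict our outcome (dating violence".

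The plan calls Aims 1 to 3 manipulation checks. It does not call 4a and 4b descriptive or exploratory, and it does not say how they are to be read if 4c points elsewhere.

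**The concern.** Three inferences are left open, and none of them is sound.

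- **Comparison.** A significant fall in one arm beside a non-significant fall in the other says little about whether the arms differ. Two arms with the same true change can easily land on opposite sides of the .05 line.
- **Attribution.** A change from baseline to follow-up eleven weeks later, within one arm, mixes any intervention effect with the passage of time, regression to the mean and changes in self-reporting. Randomisation protects only the contrast between arms.
- **Ineffectiveness.** A non-significant Aim 4a matches the stated expectation, but failure to reject is not evidence of no effect. The plan sets no margin or interval rule for how small a change would count as none. The smaller the sample, the easier it is for this expectation to be met.

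At stake is what the trial may conclude. The predictions for 4a and 4b could both be reported as met while 4c shows no difference, and the plan has no rule for that case.

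**Working it through.** **Inputs**

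- Analysed sample: 88 (Participants); allocation 1:1 (Trial design). Arm sizes are not given, so 88 / 2 = 44 per arm is assumed.
- Level and sidedness of the outcome tests: not stated; .05 appears only for covariate screening (Preliminary analyses). Two-sided .05 is assumed.
- Effect size: none stated. The Participants section names G*Power3 without inputs, so there is no planning figure to reproduce. I take a standardised within-arm fall dz (mean change / SD of change) from 0 to 0.6, **the same in both arms**.
- Outcomes: three violence types, tested separately.

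**Formulae**

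The paired t statistic has n − 1 = 43 degrees of freedom and noncentrality dz × √44 = 6.633 × dz. The two-sided critical value is 2.017.

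- S = P(t > 2.017): significant fall
- F = P(0 < t < 2.017): a fall that is not significant
- Predicted pattern for one type (arms independent): S in the MBST arm × F in the control arm
- At least one of three types, if independent: 1 − (1 − S·F)³
- All three types, if independent: (S·F)³

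**Results, 44 per arm**

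| dz | S | F | Pattern, one type | At least one of three | All three |
|---|---|---|---|---|---|
| 0 | 0.025 | 0.475 | 0.012 | 0.035 | 0.0000 |
| 0.1 | 0.095 | 0.652 | 0.062 | 0.174 | 0.0002 |
| 0.2 | 0.254 | 0.654 | 0.166 | 0.420 | 0.0046 |
| 0.3 | 0.494 | 0.482 | 0.238 | 0.558 | 0.0136 |
| 0.4 | 0.737 | 0.259 | 0.191 | 0.470 | 0.0070 |
| 0.5 | 0.900 | 0.100 | 0.090 | 0.245 | 0.0007 |
| 0.6 | 0.973 | 0.027 | 0.026 | 0.076 | 0.0000 |

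Products use unrounded S and F. Example at dz = 0.3: 0.494 × 0.482 = 0.238, and 1 − (1 − 0.238)³ = 0.558. Because F cannot exceed 1 − S, the one-type figure cannot exceed S(1 − S), hence 0.25.

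**Smaller arms.** With 26 per arm (the number fully compliant in the control arm; 24 in the MBST arm), the one-type figures over the same dz values are 0.012, 0.044, 0.112, 0.195, 0.240, 0.211 and 0.136. The peak is about the same but sits at a larger dz.

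**Non-significance in the control arm.** With 44 per arm, a true control-arm fall of dz = 0.3 fails to reach significance with probability 0.506. The result that Aim 4a expects is therefore about as likely as not when psychoeducation is followed by a real fall of that size.

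**Against a direct comparison.** I simulated 200,000 trials per setting with equal true change, using a two-sample test of change as a stand-in for Aim 4c. With 44 per arm and dz of 0.2, 0.3 and 0.4, the direct test wrongly favoured MBST in about 2.5% of trials each time. The 4a/4b pattern appeared in 16.6%, 23.9% and 19.1%. Among the trials showing the pattern, the direct test was significant in only 5.1%, 7.2% and 10.7%.

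Covariate adjustment, full information maximum likelihood (FIML) and skewed scores were not modelled.

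**The case against.** The strongest reply is that the valid test is already planned. Aim 4c has its own hypothesis and its own baseline-adjusted regression in both arms. The plan introduces 4a and 4b as looking at each intervention individually before comparing them. This stands. A reader might infer that the plan lacks a between-arm test, or derives superiority from 4a and 4b. It does neither.

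A reader might also infer that the trial will declare psychoeducation ineffective when p > .05. The text does not go that far: Aim 4a hypothesises a fall and adds an expectation about significance, and the remark on ineffectiveness describes prior evidence. No equivalence claim is made.

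Third, a reader might take the 56% as the chance that both hypotheses are confirmed when the arms do not differ. That is too strong. Both aims name physical, sexual and psychological violence together, and under independence all three show the pattern in at most about 1.4% of trials. Related subscales of one inventory are unlikely to be independent; positive correlation would lower the 56% and raise the 1.4%. The documents support no particular dz, and the risk is small at either end of the range.

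Finally, the document describes a completed study and says under Blinding that the analyses were fixed in advance and reported as stated. Deleting the recorded hypotheses now would be a retrospective rewrite.

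These points limit the size and the remedy. They do not answer the gap itself: 4a and 4b are framed as effectiveness assessments with predictions tied to significance, and no sentence ranks 4c above them.

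**Conclusion.** The concern holds as a defect in what may be concluded from Aims 4a and 4b, not in the randomised comparison. Within-arm significance neither compares the arms nor isolates an intervention effect, and a non-significant 4a cannot support ineffectiveness.

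With equal true falls, the predicted pattern occurs by chance in about 1% to 24% of trials per violence type, depending on an unknown common change. It is most likely when each within-arm test has about 50% power. These figures rest on the assumed 44 per arm, two-sided .05 and normally distributed changes. The multi-type figures also assume independence. The logical point depends on none of these.

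**What to change.** Keep the hypotheses for 4a and 4b on record as stated. In the Analysis Plan and the report:

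1. Present 4a and 4b as descriptive within-arm mean changes with 95% confidence intervals, for each violence type.
2. State that no conclusion that either intervention is effective or ineffective is drawn from their p-values.
3. State that comparative effectiveness rests on the Aim 4c between-arm estimate and its confidence interval alone, whatever 4a and 4b show.

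This needs no new data and little re-analysis. The cost is that the sponsor gives up the within-arm significance claims and must disclose the change as made after the plan was set.
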